#### **6.4 Visit 3 – Clinic Day 2 (Test Period 1, 24h Assessment)**

Participants will return to the clinic for the 24h post-dose sample collections.

- Study diary will be collected and a new diary dispensed
- Concomitant therapies and adverse events will be reviewed
- Food record will be collected and dietary compliance will be reviewed
- Weight, BMI, seated resting blood pressure and heart rate will be recorded
- Urine containers will be collected, total urine volume will be recorded and a sample for L-ascorbic acid analysis will be retained
- 24h post-dose blood sample (plasma and WBC) will be collected for the analysis of L-ascorbic acid
- Blood collection for the analysis of CBC, electrolytes (Na, K, Cl), creatinine, eGFR, AST, ALT, and bilirubin
- 7-day food records will be dispensed to record all intake of between now and their next visit

Prior to leaving the clinic participants will be reminded to maintain compliance and refrain from consuming St. John's Wort, other health supplements, foods and beverages containing vitamin C (Appendix 2) and high caffeine, alcohol, grapefruit and grapefruit juice. Participants will be reminded to maintain similar levels of physical activity throughout the study.

#### **6.5 Washout period (Day 3 to Day 10)**

Following test period 1, participants must follow a recommended food plan and record their food/drink intake for the all days preceding the next visit. Participants will start fasting 12 hours before visit 4.

The next visit will be scheduled after a 7-day washout where a two-day window (+2 days) will be allowed to accommodate scheduling. Participants will be advised on what foods to avoid during the washout period and to complete a 7-day food (+2 days if applicable) record during this time. Participants will be reminded not to consume alcohol 24h prior to their next clinic visit and that they will be required to provide a urine sample at the start of the visit. Participants will be reminded to maintain similar levels of physical activity throughout the study.

Participants will be provided with study diary to record concomitant therapies and adverse events between clinic visit 3 and visit 4. Participants will be instructed to return both the diary and 7-day food record at their next study visit.

#### **6.6 Visit 4 – Clinic Day 3 (Test Period 2, 8h In-Clinic Day)**

Participants will return to the clinic, after fasting for 12 hours (water is allowed), for the second test period assessments. Study diaries will be collected and new diaries dispensed.

Clinic Day 3 assessment includes:

- Reviewing of concomitant therapies, adverse events, and current health status
- Collecting 7-day food diary food record and reviewing dietary compliance
- Recording weight and BMI
- Recording seated resting blood pressure and heart rate
- Pre-dose blood will be collected for the analysis of CBC, electrolytes (Na, K, Cl), creatinine, eGFR, AST, ALT, and bilirubin
- Blood collection (plasma and WBC) for pre-dose (baseline, 0h) analysis of L-ascorbic acid
- Pre-dose urine collection (baseline, 0h) and total urine volume will be recorded and a sample for L-ascorbic acid analysis will be retained
- Administration of the investigational product that the participant did not receive in round 1 with 250 mL of room temperature water. Participants who receive the gummies will be instructed to chew gummies thoroughly before swallowing. Time of consumption will be recorded. Water will be permitted ad libitum 1 hour after dosing.
- Participants will be instructed to avoid reclining for 2 hours after dosing.
- Blood collection (plasma and WBC) for post-dose analysis of L-ascorbic acid at 30min 1h, 2h, 3h, 4h, 5h, 6h, 8h, 10h and 12h post-dose
- Urine collection between 0-2h post-dose and total volume will be recorded.
- Sample of 0-2h post dose urine will be retained for L-ascorbic acid analysis
- Urine collection between 2-4h post-dose and total volume will be recorded.
- Sample of 2-4h post dose urine will be retained for L-ascorbic acid analysis
- Urine collection between 4-8h post-dose and total volume will be recorded
- Sample of 4-8h post-dose urine will be retained for L-ascorbic acid analysis
- Urine collection between 8-12h post-dose and total volume will be recorded
- Sample of 8-12h post-dose urine will be retained for L-ascorbic acid analysis
- Recording of adverse events

Standardized meals devoid of vitamin C containing products will be provided to participants in the clinic (Refer to appendix 4). The following meals will be provided at the clinic: Breakfast after the 2h blood sampling, lunch after the 5h blood sampling, and supper between the 6h and 12h sampling. All food items and quantities consumed will be recorded by clinic staff for each individual participant.

Participants will remain in the clinic during the study visit from pre-dose until the 12h post-dose blood sampling. They will be allowed to watch television, use computers/laptops, read, talk, play video or board games, or sleep.

Prior to leaving the clinic participants will be reminded to maintain compliance and refrain from consuming St. John's Wort, other health supplements, foods and beverages containing vitamin C and high caffeine, alcohol, grapefruit and grapefruit juice. Participants will be reminded to maintain similar levels of physical activity throughout the study.

Participants will be provided with containers for the 12-24h urine collection.

Participants will be provided with study diary to record concomitant therapies and adverse events between the 12 and 24h clinic visit. Participants will also be provided with food record to record food or beverages consumed between the 12 and 24h clinic visit. Participants will be instructed to return the completed food record and study diary to their next visit.

Participants will return the following day for their 24h assessment (Visit 5).

### **6.7 Visit 5 - End of Study: Clinic Day 4 (Test Period 2, 24h Assessment)**

Participants will return to the clinic for the 24h post-dose sample collections.

- Study diary will be collected
- Concomitant therapies and adverse events will be reviewed
- Food records will be collected and dietary compliance will be reviewed
- Weight, BMI, seated resting blood pressure and heart rate will be recorded
- Urine containers will be collected, total urine will be recorded and a sample for L-ascorbic acid analysis will be retained
- 24h post-dose blood sample (plasma and WBC) will be collected for the analysis of L-ascorbic acid
- Blood collection for the analysis of CBC, electrolytes (Na, K, Cl), creatinine, eGFR, AST, ALT, and bilirubin

At the end of the study participants will be advised to return to their normal diet.

### **6.8 Clinical Assessments and Procedures**

Calculations or measurements of specific parameters are required as indicated in the schedule of assessments. Instructions for determining these parameters are provided in the following sections.

#### **6.8.1 Height, Weight**

Weight measurements will be performed with shoes removed, and bladder empty. Participants will be weighed on the same scale at all visits.

At least two separate measurements will be taken at each visit. If the two measurements are more than 0.5 kg (1.1 lbs) apart, a third measurement will be taken. Then the two closest values will be selected and entered in the database. However, if the 3 values are equidistant a fourth measurement will be taken and the two closest values will be selected and entered into the database.

Measurement of height will be performed with the participant's shoes removed. The participant's knees will be straightened, and head held upright.

## 6.8.2 Blood Pressure

In office, seated resting blood pressure and heart rate will be determined from 3 measurements obtained at least 1 minute apart. One arm will be chosen and used consistently throughout the study. Blood pressure will be checked in both arms at the first examination. The arm with the higher systolic blood pressure will be used throughout the study. The arm selected for use at the initial visit will be documented in the study file.

The participant should be seated comfortably with the back supported and the upper arm bared without restrictive clothing. Feet should be flat on the floor, legs will not be crossed. The participant will rest in this position for at least 5 minutes prior to the first reading.

The same recording method and the same equipment will be used for each participant throughout the study.

## 6.8.3 Compliance

Investigational product compliance calculations are not necessary in this study as the study supplements will be administered in the clinic. Participants will be asked to consume the supplements in front of the clinical coordinator. Compliance to the dietary restrictions of the protocol will be assessed using the food records completed by the participant. In the event that a participant consumes foods and/or beverages with high vitamin C content (see Appendix 2), the Qualified Investigator will determine the significance and if the participant should continue in the study.

## 6.9 Sample collection and Processing (Appendix 6 for Flow Chart)

Blood samples will be drawn from the participants at screening (Visit 1), baseline visit (Visit 2, Day 0), visit 3, visit 4 and at the end-of-study visit (visit 5) as indicated in the schedule of assessments.

Protection of volunteer confidentiality will extend to all data generated from the assaying of these samples. These samples will be alphanumerically coded and the persons (examiner blinded) performing the analysis will not be aware of the participant's identity or the allocated product they received.

Blood collected for the analysis of CBC, electrolytes (Na, K, Cl), creatinine, eGFR, AST, ALT, and bilirubin will be delivered to LifeLabs [REDACTED].

The collected whole blood will be processed to generate plasma and WBC for vitamin C analysis. Plasma and WBC will be separated and stored in light resistant cryogenic tube and stored at -80°C. Plasma samples will be delivered on dry ice to LifeLabs [REDACTED]. WBC samples will be delivered on dry ice to Mount Sinai laboratory in [REDACTED]. Stability of non-acidified vitamin C at -80°C is up to 21 days. Retainer samples will be stored at -80°C.

Urine collected for vitamin C analysis will be aliquoted into light resistant cryogenic tubes and stored at -80°C. Urine samples will be delivered on dry ice to Mount Sinai laboratory [REDACTED]. Stability of non-acidified vitamin C at -80°C is up to 21 days. Retainer samples will be stored at -80°C.

Blood Collection:

At screening (Visit 1), 13 mL of whole blood will be collected in:

1. Two 4 mL EDTA vacutainer tubes to generate plasma for:
  - a. CBC analysis (1 tube)
  - b. Hb1Ac analysis (1 tube)
2. One 5 mL SST vacutainer tube to generate serum for:
  - a. electrolytes (Na, K, Cl), creatinine, eGFR, AST, ALT, and bilirubin analysis (1 tube)

At baseline (Visit 2), 176 mL of whole blood will be collected in:

1. Twenty-two 8 mL sodium-heparin CPT™ vacutainer tubes to generate plasma and WBC for:
  - a. L-ascorbic acid analysis (total of 22 tubes – 2 tubes per time point: pre-dose (0h), 30min, 1h, 2h, 3h, 4h, 5h, 6h, 8h, 10h, and 12h post-dose)

Visit 3, 25 mL of whole-blood will be collected in:

1. One 4 mL EDTA vacutainer tube to generate plasma for:
  - a. CBC analysis (1 tube)
2. One 5 mL SST vacutainer tube to generate serum for:
  - a. electrolytes (Na, K, Cl), creatinine, eGFR, AST, ALT, and bilirubin analysis (1 tube)
3. Two 8 mL sodium-heparin CPT™ vacutainer tubes to generate plasma and WBC for:
  - a. L-ascorbic acid analysis at 24h post-dose (2 tube)

Visit 4, 185 mL of whole-blood will be collected in:

1. One 4 mL EDTA vacutainer tube to generate plasma for:
  - a. CBC analysis (1 tube)
2. One 5 mL SST vacutainer tube to generate serum for:
  - a. electrolytes (Na, K, Cl), creatinine, eGFR, AST, ALT, and bilirubin analysis (1 tube)
3. Twenty-two 8 mL sodium-heparin CPT™ vacutainer tubes to generate plasma and WBC for:
  - b. L-ascorbic acid analysis (total of 22 tubes – 2 tubes per time point: pre-dose (0h), 30min 1h, 2h, 3h, 4h, 5h, 6h, 8h, 10h, and 12h post-dose)

At the end of the study (Visit 5), 25 mL of whole-blood will be collected in:

4. One 4 mL EDTA vacutainer tube to generate plasma for:
  - a. CBC analysis (1 tube)
5. One 5 mL SST vacutainer tube to generate serum for:
  - a. electrolytes (Na, K, Cl), creatinine, eGFR, AST, ALT, and bilirubin analysis (1 tube)

6. Two 8 mL sodium-heparin CPT™ vacutainer tubes to generate plasma and WBC for:
  - a. L-ascorbic acid analysis at 24h post-dose (2 tubes)

The total blood volume collection for the laboratory assessments listed above will be approximately 424 mL, over the period from screening to end-of-study (approximately 16 days). At any study visit, blood loss per volunteer is not expected to exceed 185 mL. Additional blood samples may be collected during the study to perform repeat laboratory tests outlined in the Schedule of Assessments if needed.

A Central Laboratory, LifeLabs (██████████), will be contracted to measure safety blood (CBC, Hb1Ac, electrolytes (Na, K, Cl), creatinine, eGFR, AST, ALT, and bilirubin) and ascorbic acid content in plasma. Mount Sinai Laboratory (██████████) will also be contracted to measure L-ascorbic acid content in WBC and urine.

#### Urine Collection:

At screening (Visit 1), a urine pregnancy test will be done at the KGK Synergize clinic on females of childbearing potential.

At Baseline (Visit 2), urine will be collected for L-ascorbic acid analysis prior to dosing and total volume recorded. A sample will be retained for L-ascorbic acid analysis. Urine will be collected during the following post-dose time intervals 0-2h, 2-4h, 4-8h, and 8-12h and the total volume of each post-dose time interval will be recorded. A sample will be retained from each post-dose time interval for L-ascorbic acid analysis.

At visit 3, urine will be collected from 12-24h (a collection container will be dispensed to participants and they will be instructed to collect their urine up until their 24h post-dose appointment) and total volume will be recorded. A sample will be retained for L-ascorbic acid analysis.

At visit 4, urine will be collected for L-ascorbic analysis prior to dosing and total volume recorded. A sample will be retained for L-ascorbic acid analysis. Urine will be collected during the following post-dose time intervals 0-2h, 2-4h, 4-8h, and 8-12h and total volume of each post-dose time interval will be recorded. A sample will be retained from each post-dose time interval for L-ascorbic acid analysis.

At visit 5, Urine will be collected from 12-24h (a collection container will be dispensed to participants and they will be instructed collect their urine up until their 24h post-dose appointment) and the total volume will be recorded. A sample will be retained for L-ascorbic acid analysis.

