### 4.1 Inclusion Criteria

1. Healthy male or female from 18 and 55 years of age inclusive.
2. If female, participant is not of child bearing potential, which is defined as females who have had a hysterectomy or oophorectomy, bilateral tubal ligation or are post-menopausal (natural or surgically with > 1 year since last menstruation)  
OR  
Females of childbearing potential must agree to use a medically approved method of birth control and have a negative urine pregnancy test result. A minimum of 3-months stable dose is required for females on a hormonal birth control. Acceptable methods of birth control include:
  - Hormonal contraceptives including oral contraceptives, hormone birth control patch (████████), vaginal contraceptive ring (████████), injectable contraceptives (████████████████), or hormone implant (████████████████)
  - Double-barrier method
  - Intrauterine devices
  - Non-heterosexual lifestyle or agrees to use contraception if planning on changing to heterosexual partner(s)
  - Vasectomy of partner (shown successful as per appropriate follow-up)
3. BMI 18.5 to 29.9 kg/m^2 ( $\pm 1$  kg/m^2)
4. Healthy as determined by laboratory results and medical history
5. Agrees to maintain current level of physical activity throughout the study
6. Agrees not to donate blood for the next 3 months after completing the study
7. Agrees to avoid foods and beverages fortified with vitamin C for at least 7 days prior to enrolment and during the study
8. Agrees to avoid citrus foods, citrus juices (e.g. orange, grapefruit, lemon, lime, orange juice, grapefruit juice and lemonade), and tomato juice for at least 7 days prior to enrolment and during the study
9. Non-smoker or ex-smoker >1 year
10. Has given voluntary, written, informed consent to participate in the study
11. Agrees to avoid high caffeine and alcohol intake 72 hours prior to in-clinic test days and during the 24-hour in-clinic test days

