### 4.2 Exclusion Criteria

1. Women who are pregnant, breast feeding, or planning to become pregnant during the trial

2. Duodenal or gastric ulcer, gastritis, hiatus hernia, or GERD within past 3 months
3. History irritable bowel syndrome and related disorders
4. Significant gastrointestinal disease (examples include but are not limited to Celiac disease)
5. History of malabsorption
6. Unstable medical conditions as determined by the Qualified Investigator
7. Blood pressure greater than 150/90 mmHg
8. Cancer except skin cancers completely excised with no chemotherapy or radiation following and with a negative follow up. Volunteers with cancer in full remission for more than 5 years after diagnosis are acceptable.
9. Clinically significant abnormal laboratory results at screening
10. Metabolic disease or chronic diseases (examples include and not limited to hyperlipidemia, hypertension, and hypercholesterolemia)
11. Type I or Type II diabetes
12. History of kidney stones
13. Use of prescription or over the counter products known to interact with vitamin C within 72 hours of enrolment and during the trial such as aspirin and NSAIDs (including acetaminophen containing medications), aluminum (found in most antacids),, iron, and proton pump inhibitors
14. Use of acute over the counter medication within 72 hours of test product dosing
15. Use of tobacco products within the last year
16. More than 2 alcoholic drinks per day
17. Drug abuse within 1 year of enrolment
18. Use of medicinal marijuana
19. Immunocompromised individuals such as individuals that have undergone organ transplantation or individuals diagnosed with human immunodeficiency virus (HIV)
20. Individuals who have planned surgery during the course of the trial
21. St. John's wort in the last 30 days prior to enrolment and during the study
22. Use of vitamin C, multivitamins containing vitamin C, or foods or beverages fortified with vitamin C and other natural health products containing vitamin C within 7 days of enrolment and during the study
23. Consumption of citrus foods, citrus juices (e.g. orange, grapefruit, lemon, lime, orange juice, grapefruit juice and lemonade), and tomato juice within 7 days of enrolment and during the study
24. Use of anticoagulants (warfarin), barbiturates, tetracycline antibiotics, beta-blockers, cyclosporine, prednisone, tricyclic antidepressants, diuretics and nitrate medications (including daily use of low-dose Aspirin)

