#### **Clinical reasons**

A participant may be withdrawn from the study if, in the opinion of the Qualified Investigator, it is not in the participant's best interest to continue. Any participant who experiences a serious adverse event (SAE) may be withdrawn from the trial at the discretion of the Qualified Investigator. A participant will also be withdrawn due to adverse events causing clinically significant illness or the need for prohibited medication(s) during the trial. Any female participant who becomes pregnant during the course of the trial will be withdrawn.

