### 6.1 Visit 1 – Screening (Day -28 to Day -8)

At screening, a volunteer Informed Consent Form will be given to the potential participant. The volunteer will read the information carefully and will be given the opportunity to seek more information if needed. The volunteer will also be provided with the option of taking the consent form home to review prior to making his or her decision. If agreeable, the volunteer will sign the consent form and receive a duplicate. Once consent has been obtained, the screening visit will proceed. After the volunteer has signed the informed consent, the screening number will be assigned sequentially and entered in the Screening and Enrolment Log. Screening numbers will be allocated in the chronological order of the volunteer signing the informed consent. Participants will be provided with a list of meal items to choose from during the 8-h clinic visits.

Visit 1 assessments include:

- Reviewing of medical history, concomitant therapies, and current health status
- Urine pregnancy test for females of childbearing potential and participants that are not post-menopausal
- Recording weight, height, and BMI
- Recording seated resting blood pressure and heart rate
- Assessing inclusion and exclusion criteria
- Blood collection for the analysis of CBC, electrolytes (Na, K, Cl), HbA1c, creatinine, estimated glomerular filtration rate (eGFR), aspartateaminotransferase (AST), alanine aminotransferase (ALT), and bilirubin
- Dispensing 7-day food record and instructing on completion
- Nutrition counselling
- Instructing volunteers to maintain their current dietary habits but to refrain from consuming St. John's Wort, health supplements, foods and beverages containing vitamin C (Refer to Appendix 3), tomato juice, citrus food, and juice (orange, grapefruit, lemon, lime, orange juice, grapefruit juice and lemonade) 7 days prior to their next visit.
- Volunteers will be instructed to fast (water is allowed) for 12 hours prior to their next visit and avoid alcohol for 24 hour prior to coming to the clinic

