## **6.3 Visit 2 – Baseline: Clinic Day 1 (Test Period 1, 8h In-Clinic Day)**

Eligible participants will return to the clinic after fasting for 12 hours (only water is allowed) for baseline assessments.

Baseline assessments include:

- Reviewing of concomitant therapies and current health status
- Physical exam
- Assessing of inclusion and exclusion criteria
- Collecting 7-day food record and reviewing dietary compliance
- Randomizing eligible participants

- Recording weight and BMI
- Recording seated resting blood pressure and heart rate
- Blood collection (plasma and WBC) for pre-dose baseline (0h) analysis of L-ascorbic acid
- Pre-dose urine collection (baseline 0h) and total urine volume will be recorded and a sample for L-ascorbic acid analysis will be retained
- Following randomization and collection of pre-dose samples, Investigational product administration with 250 mL of room temperature water and recording of consumption time. Participants who receive the gummies will be instructed to chew gummies thoroughly before swallowing. Water will be permitted ad libitum 1-hour after dosing.
- Participants will be instructed to avoid reclining for 2 hours after dosing.
- Blood collection (plasma and WBC) for post-dose analysis of L-ascorbic acid at 30min, 1h, 2h, 3h, 4h, 5h, 6h, 8h, 10h and 12h post-dose
- Urine collection between 0-2h post-dose and total volume will be recorded.
- Sample of 0-2h post dose urine will be retained for L-ascorbic acid analysis
- Urine collection between 2-4h post-dose and total volume will be recorded.
- Sample of 2-4h post dose urine will be retained for L-ascorbic acid analysis
- Urine collection between 4-8h post-dose and total volume will be recorded
- Sample of 4-8h post dose urine will be retained for L-ascorbic acid analysis
- Urine collection between 8-12h post-dose and total volume will be recorded
- Sample of 8-12h post dose urine will be retained for L-ascorbic acid analysis
- Recording of adverse events

Standardized meals devoid of vitamin C containing products will be provided to participants in the clinic (Refer to appendix 4). The following meals will be provided at the clinic: Breakfast after the 2h blood sampling, lunch after the 5h blood sampling, and supper between the 6h and 12h sampling. All food items and quantities consumed will be recorded by clinic staff for each individual participant.

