### Schedule of Assessments

Procedures/assessments	Visit 1 Screening		Visit 2 Baseline 0-12 hour	Visit 3 24 hour		Visit 4 0-12 hour	Visit 5 24 hour End of study
	1 st study period		1 st study period	1 st study period		2 nd study period	2 nd study period
Informed Consent	X						
Review of Inclusion/Exclusion criteria	X		X				
Review of medical history/current health status	X		X			X	
Review of concomitant therapies	X		X	X		X	X
Review adverse events				X		X	X
Height*, weight, blood pressure and heart rate	X		X	X		X	X
Randomization			X				
Physical Exam			X				
Nutrition counselling	X						
Laboratory Tests				X			
Blood sample collection for CBC, electrolytes, HbA1c*, creatinine, eGFR, AST, ALT, and bilirubin analysis	X					X	X
Urine pregnancy test	X						
Blood samples: Pre-dose (t=0) and Post-dose (30 min, 1h, 2h, 3h, 4h, 5h, 6h, 8h, 10 h, 12 h) for L-Ascorbic Acid analysis			X			X	
Blood samples: 24 hours for L-Ascorbic Acid analysis				X			X
Pre-dose Urine sample for L-Ascorbic Acid analysis			X			X	
Post-dose urine samples: 0-2h, 2-4h, 4-8h, 8-12h post-dose L-Ascorbic Acid analysis			X			X	
Dispense urine collection kits for 8-24h urine collection: L-ascorbic acid			X			X	
Return post-dose urine sample collection: 12-24h post-dose L-Ascorbic Acid analysis				X			X
IP or Comparator Dispensed			X			X	
Breakfast, lunch, and dinner provided			X			X	
Study diary dispensed			X	X		X	
Study diary returned				X		X	X
24h-food record dispensed			X			X	
24h-food record returned				X			X
7-day food record dispensed	X			X			
7-day food record returned				X			

\* Will only be measured at screening visit (Visit 1)

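### No pregnancy test is scheduled after Visit 1, so at both doses the pregnancy exclusion and withdrawal rules rest on a screening result, agreed contraception and self-report

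*Combined protocol and SAP*

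**What the plan says.** Non-pregnancy is a condition of entry and of continuing:

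- Inclusion criterion 2 (4.1): "Females of childbearing potential must agree to use a medically approved method of birth control and have a negative urine pregnancy test result". It sets no interval between the test and dosing.
- Exclusion criterion 1 (4.2): "Women who are pregnant, breast feeding, or planning to become pregnant during the trial".
- Early withdrawal, clinical reasons (4.4): "Any female participant who becomes pregnant during the course of the trial will be withdrawn".

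The test appears in three places, each time at screening only:

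- Section 6.1, Visit 1 assessments: "Urine pregnancy test for females of childbearing potential and participants that are not post-menopausal".
- Section 6.9, Urine Collection: "At screening (Visit 1), a urine pregnancy test will be done at the KGK Synergize clinic on females of childbearing potential".
- Appendix 1: the row "Urine pregnancy test" has one mark, under Visit 1.

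Urine is also taken before each dose, for ascorbic acid. Section 6.3 has "Pre-dose urine collection (baseline 0h) and total urine volume will be recorded", and 6.6 has the equivalent item for Visit 4.

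**The concern.** A test taken at screening cannot show a conception that happens later. A woman screened early in the window can reach the Visit 2 eligibility check with a result about four weeks old. She can then be dosed in both periods without another test. The protocol has an explicit rule for pregnancy during the trial but schedules no test that would reveal one. By contrast, blood pressure and heart rate are repeated at every visit, and blood count and chemistry at Visits 3, 4 and 5. What is at stake is participant safety and the integrity of eligibility; the primary analysis is not affected.

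**Working it through.** **Inputs**

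- Screening window: Day -28 to Day -8 (6.1).
- First dose: Visit 2. Section 6.9 calls it Day 0. The Clinic Day 1 label in 6.3 and a second washout that starts on Day 3 (6.5) point to Day 1. Both are carried through.
- Second dose: Visit 4, after a 7-day washout headed Day 3 to Day 10, with a window of +2 days (6.5). Depending on how the seven days are counted, the nominal visit falls on Day 9, 10 or 11, and the latest possible day is 11 + 2 = Day 13.
- Blood volumes by visit (6.9): 13, 176, 25, 185 and 25 mL.
- Women planned: 18 (Appendix 5, 18 participants per sex).

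**Age of the test result at dosing**

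The documents state no such interval, so there is no figure of theirs to reproduce. The formula is: gap = dose day − screening day, less 1 if the calendar has no Day 0.

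| Screening | Dose | With a Day 0 | No Day 0 |
|---|---|---|---|
| Day -28 | first, Day 0 | 0 + 28 = 28 | not applicable |
| Day -28 | first, Day 1 | 1 + 28 = 29 | 29 − 1 = 28 |
| Day -28 | second, Day 9 | 9 + 28 = 37 | 37 − 1 = 36 |
| Day -28 | second, Day 13 | 13 + 28 = 41 | 41 − 1 = 40 |
| Day -8 | first, Day 0 | 0 + 8 = 8 | not applicable |
| Day -8 | first, Day 1 | 1 + 8 = 9 | 9 − 1 = 8 |
| Day -8 | second, Day 9 | 9 + 8 = 17 | 17 − 1 = 16 |
| Day -8 | second, Day 13 | 13 + 8 = 21 | 21 − 1 = 20 |

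The result is therefore 8 to 29 days old at the first dose and 16 to 41 days old at the second. About 40 days is a maximum: it needs screening on Day -28 and a Visit 4 at the end of its window.

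**The one related duration in the plan**

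Section 6.9 gives about 16 days from screening to end of study. That equals 7 + 1 + 7 + 1, two washouts and two 24-hour periods. With Visit 5 one day after the second dose, the 6.1 window gives 17 days (Day -8 screening, second dose Day 9, no Day 0) to 42 days (Day -28 screening, second dose Day 13, with a Day 0). The stated figure is close to the shortest schedule only, so it does not show that the gap is small.

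**Checks available at each dose**

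| Check | Visit 2 | Visit 4 |
|---|---|---|
| Inclusion and exclusion criteria re-assessed | yes | no |
| Current health status reviewed | yes | yes |
| Adverse events reviewed before dosing | no | yes |
| Pre-dose urine collected | yes | yes |
| Pregnancy test | no | no |

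**What follows the only test**

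Both doses, and 176 + 25 + 185 + 25 = 411 mL of the 13 + 411 = 424 mL of blood.

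**The case against.** The strongest reply is that the plan is consistent and not without safeguards. All three places put the test at Visit 1, no section promises a pre-dose test, and inclusion 2 sets no maximum age for the result. Women of childbearing potential must use an approved contraceptive method, stable for at least three months if hormonal. Criteria are re-assessed at Visit 2, health status is reviewed at Visits 2 and 4, and participants are asked about problems at each visit (7.1.1). Withdrawal under 4.4 does not depend on a test.

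Most of this stands, and it limits the point. A reader might infer that neither the exclusion nor the withdrawal rule can be applied at dosing. The documents do not support that: exclusion 1 is formally re-assessed at Visit 2, and a pregnancy that is reported or found by other means triggers withdrawal at any time. Nor do the passages on test timing contradict each other; this is a design choice.

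The size also needs care. Eighteen is an upper bound for the planned 36, because inclusion 2 also admits women who are post-menopausal or surgically sterile. The 411 mL shows how much of the study follows the test; it does not measure risk. The documents give no probability of pregnancy and no pregnancy-specific harm.

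What the reply does not answer is that contraception and self-report do not reveal a pregnancy the participant has not recognised, and that Visit 4 lacks even the eligibility re-check.

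**Conclusion.** The point holds in a limited form. No pregnancy test verifies status before either dose, and after Visit 1 the protocol's own rules depend on an ageing result, contraception and what the participant reports. The result may be 28 to 29 days old at the first dose and up to about 40 days old at the second, falling to 8 to 9 and 16 to 21 days with screening on Day -8. The gap is wider at Visit 4.

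These figures assume the day labels in 6.1, 6.5 and 6.9 as read above; the choice between Day 0 and Day 1 moves each by at most one day. At most 18 of the planned 36 participants are concerned, and no harm can be quantified from the documents. This is an inexpensive safety improvement and has no bearing on sample size, error rates or the analysis of the primary outcome.

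**What to change.** - In 6.3, 6.6, 6.9 and Appendix 1, add the same urine pregnancy test at Visits 2 and 4, run on the pre-dose urine already collected.
- In 6.3, which lists randomisation ahead of the pre-dose urine, move that collection and the reading of the result before randomisation. At Visit 4, read the result before dosing.
- Handle a positive result under the exclusion and withdrawal provisions already in 4.2 and 4.4. No new clinical rule is needed.
- Reconcile who is tested. Section 6.1 adds participants who are not post-menopausal, whereas 6.9 names only those of childbearing potential. A pre-menopausal woman with a tubal ligation, who is not of childbearing potential under inclusion 2, would be tested under 6.1 but not under 6.9.
- At the same time, reconcile the 16-day duration in 6.9 with the screening window in 6.1, and the Day 0 and Day 1 labels for Visit 2.

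The cost is up to two strips per woman of childbearing potential, so at most 18 × 2 = 36 extra tests for the planned sample. It also takes a few minutes before each dose and a small re-ordering of Visit 2. No new sample, visit or staff is needed, since the site already runs this test in its clinic. Any withdrawal falls under the existing replacement rule that protects the target of 30 completers (4.4 and 8.3.1).
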